#### **6.12.2** Secondary Endpoints

# 6.12.2.1 Change in mean WHO Ordinal Scale for Clinical Improvement at Day 15, Day 22 and Day 29

The mean change in WHO Ordinal Scale for Clinical Improvement from baseline to Day 15, Day 22 and Day 29 will be assessed.

Baseline for WHO Ordinal Scale is the last available record up to and including Day 1. If subject died or was discharged from the hospital prior to Day 15, 22 or 29 and WHO Ordinal Scale for Clinical Improvement is not collected or record is otherwise missing at those timepoints then the last available observation before or at the time of death/discharge will be carried forward.

Analysis will be performed using two different approaches, including the LOCF values and excluding LOCF values. Further, these analyses will be repeated using separate baseline definition. As the time of WHO Ordinal Scale is collected it cannot be definitely confirmed if Day 1 record was taken before or after start of study treatment. Sensitivity analysis will be performed using the WHO Ordinal Scale from Screening record.

Descriptive statistics (n, mean, standard deviation, median, minimum and maximum) will be summarized for absolute values and change from baseline by treatment group and visit.

Change from baseline will be analyzed using mixed model for repeated measures (MMRM) including treatment, visit and treatment-by-visit interaction as fixed effects, and study site, remdesivir use (No/Yes), dexamethasone use (No/Yes) and WHO Ordinal Scale for Clinical Improvement at baseline as covariates. The resulting F-tests will be based on Kenward-Roger's adjusted degrees of freedom. Subject effect will be assumed to be random and an unstructured covariance structure will be used for within subject variation. If this model does not converge then the following covariance matrices will be used in order until the model converges: Toeplitz, first-order autoregressive, and compound symmetry. Least squares means, standard errors, 95% confidence intervals and p-values for treatments and treatment differences at each visit (study days 15, 22, 29, 45 and 60) will be presented.

QMD Ref: Worldwide-TMP-ST-005-7.0 Effective: 12Aug2019 Governing QMD: Worldwide-SOP-ST-0		
Confidentiality Statement		
This document is the property of Worldwide Clinical Trials Inc. and may not be duplicated, copied, altered or removed from company without		
prior approval from Worldwide Quality Assurance or in compliance with Worldwide Standard Operating Procedures.		

Worldwide Clinical Trials Controlled Quality Management Document		
WORLDWIDE CLINICAL TRIALS	Sponsor:	Veru Inc.
	Protocol Number:	V0211901
STATISTICAL ANALYSIS PLAN. PHASE 2-3-4		

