6.2.2 Exclusion Criteria

Any of the following conditions are cause for exclusion from the study:

- 1. Known hypersensitivity or allergy to colchicine
- 2. Participation in any other clinical trial of an experimental treatment for COVID-19. Convalescent plasma and remdesivir are allowed in this study.

- 3. Concurrent treatment with other experimental agents with actual or possible direct acting antiviral activity against COVID-19 is prohibited < 24 hours prior to study drug dosing (except standard of care). Remdesivir and convalescent plasma are allowed in the study.
- Requiring ventilation + additional organ support pressors, RRT, ECMO (WHO Ordinal Scale for Clinical Improvement – Score of 7) and patients requiring ventilation with a WHO Ordinal Scale for Clinical Improvement – Score of 6 for >5 days at screening.
 - Patients on ventilation with a WHO Ordinal Scale for Clinical Improvement Score of 5 (non-invasive ventilation or high-flow oxygen) are allowed into the study.
 - Patients on ventilation with a WHO Ordinal Scale for Clinical Improvement Score of 6 (intubation and mechanical ventilation) for less than five (5) days are allowed into the study.
- 5. Alanine Aminotransferase (ALT) or aspartate aminotransferase (AST) >2 X upper limit of normal (ULN)
- 6. Total bilirubin > ULN
- 7. Creatinine clearance < 60 mL/min
- 8. Documented medical history of liver disease, including but not limited to, prior diagnosis of hepatitis of any etiology, cirrhosis, portal hypertension, or confirmed or suspected esophageal varices
- 9. Moderate to severe renal impairment
- 10. Hepatic impairment
- 11. History of hepatitis
- 12. Any comorbid disease or condition (medical or surgical) which might compromise the hematologic, cardiovascular, endocrine, pulmonary, renal, gastrointestinal, hepatic, or central nervous system; or other conditions that may interfere with the absorption, distribution, metabolism or excretion of study drug, or would place the subject at increased risk
- 13. Participants must agree to refrain from prolonged exposure to the sun or agree to use at least SPF 50 on all exposed skin and protective clothing during prolonged sun exposure throughout participation in this study and/or treatment with VERU-111.

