# 6.12.1 Primary Endpoint

QMD Ref: Worldwide-TMP-ST-005-7.0 Effective: 12Aug2019 Governing QMD: Worldwide-SOP-ST-		
Confidentiality Statement		
This document is the property of Worldwide Clinical Trials Inc. and may not be duplicated, copied, altered or removed from company without prior approval from Worldwide Quality Assurance or in compliance with Worldwide Standard Operating Procedures.		

REF: Worldwide-TMP-QA-001f-1.3

Worldwide Clinical Trials Controlled Quality Management Document		
WORLDWIDE CLINICAL TRIALS	Sponsor:	Veru Inc.
	Protocol Number:	V0211901
STATISTICAL ANALYSIS PLAN. PHASE 2-3-4		

The primary endpoint for the study is the proportion of subjects that are alive without respiratory failure at Day 29. Respiratory failure is defined as endotracheal intubation and mechanical ventilation, extracorporeal membrane oxygenation, high-flow nasal cannula oxygen delivery, noninvasive positive pressure ventilation, clinical diagnosis of respiratory failure with initiation of none of these measures only when clinical decision making is driven solely by resource limitation.

This analysis will compare the percentage of subjects that are alive without respiratory failure on Day 29 (responder).

Responders are subjects who have Grade 0-4 on the WHO Ordinal Scale for Clinical Improvement on Day 29. If subject was discharged from the hospital prior to Day 29 and WHO Ordinal Scale for Clinical Improvement is not collected at Day 29 then the last available observation before or at the time of discharge will be carried forward.

Non-responders are subjects who died before Day 29 or has Grade 5, 6, 7, or 8 on the WHO Ordinal Scale for Clinical Improvement on Day 29.

The number and percentage of responders will be summarized by treatment group. Responders will be analyzed using a logistic regression model. This model will include treatment as a factor, and study site, remdesivir use (No/Yes), dexamethasone use (No/Yes) and WHO Ordinal Scale for Clinical Improvement at baseline as a covariates. Odds ratios, standard errors, 95% confidence intervals and p-values for the treatment difference will be presented.

The primary analysis will be performed on the ITT population. A sensitivity analysis will be performed repeating the analysis on the EE population.

Example SAS code for the analysis is as follows:

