#### 6.12.2.4 Days on mechanical ventilation

Mechanical ventilation is defined as subject having 'Intubation and mechanical ventilation' or 'Ventilation + additional organ support – pressors, RRT, ECMO'.

'Days on mechanical ventilation' will be summarized using descriptive statistics (n, mean, standard deviation, median, minimum and maximum) by treatment group.

'Days on mechanical ventilation' will be the number of days on mechanical ventilation up to Day 29. If subject dies early in the study and was on mechanical ventilation at the time of the death then it is assumed that subject was on mechanical ventilation up to Day 29. A sensitivity analysis will be performed assigning the worst possible endpoint score for deaths (i.e., considered to be on mechanical ventilation from baseline up to Day 29 and setting days on mechanical ventilation to 29).

Treatment comparison will be based on analysis of covariance (ANCOVA) model including treatment as a factor, and study site, remdesivir use (No/Yes), dexamethasone use (No/Yes) and WHO Ordinal Scale for Clinical Improvement at baseline as covariates. Treatment difference, standard error, 95% confidence interval and p-value will be presented.

Example SAS codes for the analysis are as follows:

#### 6.12.2.5 All-cause mortality at Day 15, Day 22, and Day 29

The number and percentage for all-cause mortality will be summarized by treatment group and visit.

These endpoints will be analyzed using the same methodology as for the primary endpoint.

Responders are subjects who are alive at the time of the visit.

Non-responders are subjects who died before the visit.

Separate analysis will be performed for each visit.

QMD Ref: Worldwide-TMP-ST-005-7.0 Effective: 12Aug2019	Governing QMD: Worldwide-SOP-ST-001	
Confidentiality Statement		
This document is the property of Worldwide Clinical Trials Inc. and may not be duplicated, copied, altered or removed from company without		
prior approval from Worldwide Quality Assurance or in compliance with Worldwide Standard Operating Procedures		

Worldwide Clinical Trials Controlled Quality Management Document		
WORLDWIDE CLINICAL TRIALS	Sponsor:	Veru Inc.
	Protocol Number:	V0211901
STATISTICAL ANALYSIS PLAN. PHASE 2-3-4		

Responder rates and differences between treatment groups in responder rates will be calculated as sensitivity analysis using the same methodology as for the primary endpoint.

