# **6.12.3** Exploratory Endpoints

#### 6.12.3.1 Area under curve (AUC) of WHO Ordinal Scale for Clinical Improvement

Area under curve (AUC) of WHO Ordinal Scale for Clinical Improvement will be calculated from baseline up to Day 15 using trapezoidal rule. For each subject all available measurements up to study day 15 are included in the calculations. If subject does not have record on Day 15 then the last observation carried forward (LOCF) will be used. If a patient dies on Day 10, then they would be an 8 from Day 10 to Day 15. If the patient is discharged as a 2 on Day 5 then they would be a 2 from Day 5 to Day 15.

Actual collection times will be used in the calculations.

AUC will be summarized by treatment group and listed together with WHO Ordinal Scale for Clinical Improvement.

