# STATISTICAL ANALYSIS PLAN. PHASE 2-3-4

Table Number	Table Title	Included in Preliminary Analysis	Included in DSMB (Table No.)	Validation Method	Shell Number (if repeat)
14.1.5.3	Standard of Care (ITT Population)			IP	
14.2	Efficacy Data				
14.2.1	Primary Efficacy Endpoint				
14.2.1.1	Proportion of Subjects Alive and Free of Respiratory Failure by Visit (ITT Population)	Yes		IP	
14.2.1.2	Logistic Regression for Proportion of Subjects Alive and Free of Respiratory Failure by Visit (ITT Population)	Yes		Stat IP	
14.2.1.2a	Responder Rates for Proportion of Subjects Alive and Free of Respiratory Failure by Visit (ITT Population)			Stat IP	
14.2.1.3	Proportion of Subjects Alive and Free of Respiratory Failure by Visit (EE Population)			IP	14.2.1.1
14.2.1.4	Logistic Regression for Proportion of Subjects Alive and Free of Respiratory Failure by Visit (EE Population)			Stat IP	14.2.1.2
14.2.2- 14.2.11	Secondary Efficacy Endpoints				
14.2.2.1	Descriptive Statistics for WHO Ordinal Scale for Clinical Improvement by Visit - With LOCF values (ITT Population)	Yes		IP	
14.2.2.2	Mixed Model for Repeated Measures (MMRM) for Change from Baseline in WHO Ordinal Scale for Clinical Improvement - With LOCF values (ITT Population)	Yes		Stat IP	
14.2.2.3	Descriptive Statistics for WHO Ordinal Scale for Clinical Improvement by Visit - Without LOCF values (ITT Population)			IP	14.2.2.1
14.2.2.4	Mixed Model for Repeated Measures (MMRM) for Change from Baseline in WHO Ordinal Scale for Clinical Improvement - Without LOCF values (ITT Population)			Stat IP	14.2.2.2
14.2.2.5	Descriptive Statistics for WHO Ordinal Scale for Clinical Improvement by Visit - With LOCF values - Screening as Baseline (ITT Population)	Yes		IP	14.2.2.1
14.2.2.6	Mixed Model for Repeated Measures (MMRM) for Change from Baseline in WHO Ordinal Scale for Clinical Improvement - With LOCF values - Screening as Baseline (ITT Population)	Yes		Stat IP	14.2.2.2
14.2.2.7	Descriptive Statistics for WHO Ordinal Scale for Clinical Improvement by Visit - Without LOCF values - Screening as Baseline (ITT Population)			IP	14.2.2.1
14.2.2.8	Mixed Model for Repeated Measures (MMRM) for Change from Baseline in WHO Ordinal Scale for Clinical Improvement - Without LOCF values - Screening as Baseline (ITT Population)			Stat IP	14.2.2.2
14.2.2.9	Area Under Curve of WHO Ordinal Scale for Clinical Improvement (ITT Population)			IP	

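### SAP 6.12.2.1 has no explicit rule that death scores 8 on the WHO scale, so its no-LOCF analyses drop deaths that lack a visit record

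*SAP*

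**What the plan says.** SAP 3.2 defines the scale with death as 8. SAP 6.12.2.1 covers patients who died or were discharged before Day 15, 22 or 29 and have no score at that visit: "then the last available observation before or at the time of death/discharge will be carried forward". The next paragraph says: "Analysis will be performed using two different approaches, including the LOCF values and excluding LOCF values". Both versions are run with two baseline definitions, which gives eight tables. The no-LOCF ones are 14.2.2.3, 14.2.2.4, 14.2.2.7 and 14.2.2.8.

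The model is an MMRM. Its least squares means and treatment differences "at each visit (study days 15, 22, 29, 45 and 60) will be presented", whereas the carry-forward sentence names only Days 15, 22 and 29.

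Death is explicit elsewhere:

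- Primary endpoint (SAP 6.12.1): "Non-responders are subjects who died before Day 29".
- AUC of the same scale (SAP 6.12.3.1): "If a patient dies on Day 10, then they would be an 8 from Day 10 to Day 15".
- Days on mechanical ventilation (SAP 6.12.2.4): "A sensitivity analysis will be performed assigning the worst possible endpoint score for deaths".

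SAP 6.2.9 tabulates only scheduled post-baseline values and disregards unscheduled ones. SAP 6.12.4 treats all secondary endpoints as descriptive.

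**The concern.** By the wording of 6.12.2.1, the score filled in for a patient who died is an LOCF value, so the no-LOCF version removes it. An 8 entered on the date of death may not help. Deaths usually fall between scheduled visits, and under 6.2.9 an unscheduled record can be read as disregarded.

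The SAP does not name a missing-data assumption, but a likelihood MMRM on the remaining records relies on missing at random. A patient who has died is not missing in that sense, because the score is known and is the worst possible. Dropping it flatters the arm with more deaths. Benefit is understated if more placebo patients die, and harm is understated if more VERU-111 patients die. The no-LOCF run is then not a clean check on the LOCF run, since it changes the handling of deaths as well as of living patients without a score.

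The LOCF version has two smaller gaps. Its wording most naturally gives 8 but also permits a lower score recorded before death, and it gives no rule for Days 45 and 60.

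**Working it through.** The plan states no figure for this endpoint, so there is none to reproduce. The 20 per arm comes from SAP 5 and death = 8 from SAP 3.2. Death rates, survivors' scores and scores before death are assumptions.

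**Step 1: effect of dropping one death, raw means.** Let the 19 survivors have mean baseline b and mean score m, and let the patient who died have baseline b + g and score 8.

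- Mean change with the death kept: [19(m - b) + (8 - b - g)]/20
- Mean change with the death dropped: m - b
- Difference: [(8 - m) - g]/20

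For m = 2, 3, 4 this is 0.30, 0.25, 0.20 with g = 0, and 0.20, 0.15, 0.10 with g = 2. A gap of 2, such as baseline 6 against 4, is possible because patients with a "Score of 6 (intubation and mechanical ventilation) for less than five (5) days are allowed into the study" (Protocol 6.2.2).

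With 3 placebo deaths, 1 VERU-111 death, m = 3 and the same change among survivors in both arms, the difference lost is (3 - 1) x 0.25 = 0.50 for g = 0, or (3 - 1) x 0.15 = 0.30 for g = 2. This is an extreme case: every dropped patient has no other score in the model.

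**Step 2: a repeated-measures model.** The simulation fitted an MMRM by maximum likelihood with unstructured covariance at Days 15, 22 and 29 and baseline score as covariate, with 300 runs per row. Assumptions:

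- Baseline 4, 5, 6 with probability 0.50, 0.35, 0.15
- Survivors' mean scores about 4, 3, 2 at the three visits, with no treatment effect among survivors
- Score before death 5, 6, 7 with probability 0.2, 0.4, 0.4

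Day 29 difference, VERU-111 minus placebo:

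| Mortality (VERU-111 vs placebo), days of death | Death = 8 | Score before death carried | Death dropped |
|---|---|---|---|
| 10% vs 30%, Days 3-28 | -1.27 | -0.88 | -0.22 |
| 10% vs 30%, all before Day 15 | -1.11 | -0.75 | +0.04 |
| 10% vs 30%, all after Day 15 | -1.17 | -0.80 | -0.32 |
| 10% vs 20%, Days 3-28 | -0.63 | -0.43 | -0.09 |
| 20% vs 20%, Days 3-28 | 0.03 | 0.00 | -0.02 |

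Monte Carlo standard errors are 0.02 to 0.05. The first column can be checked by hand. With 2 and 6 deaths of 20 and survivors at 2, the arm means are (2 x 8 + 18 x 2)/20 = 2.6 and (6 x 8 + 14 x 2)/20 = 3.8, a difference of -1.2. The three 10% vs 30% rows vary around that value by simulation error.

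For deaths after Day 15, earlier poor scores let the model recover part of the loss. For deaths before Day 15 there is nothing to recover from. If the LOCF wording is read as carrying a lower score from before death, the difference shrinks by about 30% (1 - 0.88/1.27 = 0.31). In raw means that is (8 - s)/20 per death: 0.20, 0.15, 0.10, 0.05 for s = 4, 5, 6, 7, and 0 if the 8 is used.

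**Step 3: the no-LOCF version also drops discharged patients.** Assume 20 per arm, equal baselines, 2 deaths per arm, discharged patients at 2 with no record (12 on VERU-111, 6 on placebo) and inpatients at 4 (6 and 12).

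- All patients: (16 + 24 + 24)/20 - (16 + 12 + 48)/20 = 3.20 - 3.80 = -0.60
- No-LOCF as written, inpatients only: 4 - 4 = 0.00
- No-LOCF with deaths scored 8 and discharged patients still dropped: (16 + 24)/8 - (16 + 48)/14 = 5.00 - 4.57 = +0.43

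Scoring deaths as 8 therefore does not by itself make the no-LOCF version sound, and the difference can take the wrong sign.

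**The case against.** The strongest reply is that death is already on this scale. An observation at the time of death is an 8, and the AUC section illustrates exactly that after stating its LOCF rule. On this reading the LOCF tables already give deaths the worst score, and they are the only ones of the eight marked for the preliminary analysis. This stands as the natural reading, so the LOCF gap is an ambiguity and not a demonstrated error. It does not help the no-LOCF tables, where the carried 8 is removed.

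A reader might infer more than the documents support:

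- *That an 8 can never enter the analysis.* An 8 recorded at a scheduled visit is used in both versions. The documents do not say whether sites record one at death.
- *That the absence of a worst-score table, as planned for ventilation and ICU days, is an inconsistency.* Those endpoints do not contain death and need such a version. This scale contains it. Protocol 9.4 likewise promises rules for endpoints that do not directly incorporate death.
- *That a patient who dies before Day 15 is certainly absent from the model.* The listed days are those at which results are presented. Earlier scores may exist, and the example SAS code for this section was not readable in the text available.

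It is also fair that Days 45 and 60 lie outside the endpoint, which is defined at Days 15, 22 and 29, and that the affected output is supportive.

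**Conclusion.** The point holds: followed as written, the four no-LOCF tables discard known deaths that have no visit record, and the rule for the LOCF tables needs one clarification. In the simulated 10% vs 30% cases, dropping deaths removed about 73% of the difference with deaths after Day 15 (1 - 0.32/1.17), 83% with deaths over Days 3-28 (1 - 0.22/1.27), and all of it within simulation error with deaths before Day 15. These sizes rest on assumed mortality and scores, no treatment effect among survivors, and no usable 8 at the visit. The documents give no death rates.

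A total loss should not be presented as the expected result, because it needs all deaths before Day 15 and no earlier modelled score. Nor does this threaten the trial's main conclusions: the endpoint is descriptive, the no-LOCF tables are outside the preliminary set, and the primary, mortality and AUC analyses count deaths explicitly. The importance is between a minor clarification and a change that should be made.

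**What to change.** In SAP 6.12.2.1:

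1. State that from the date of death the WHO score is 8 at every later analysed visit (Days 15, 22, 29, 45 and 60), in both versions and for both baseline definitions, as a known value and not as LOCF. This matches 6.12.3.1.
2. Name the LOCF version with death = 8 as the main analysis of this endpoint.
3. Label the no-LOCF version supportive only. Report by arm and visit how many discharged patients it excludes, and note that with deaths kept and discharged patients dropped its difference can be biased in either direction.

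The cost is a few sentences and one count per arm and visit. Protocol 8.10 already collects the date of death, and the AUC endpoint already needs the same derivation.

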#### Example SAS code for the analysis is as follows:

# 6.12.2.2 Proportion of subjects that are Grade 5, 6, 7, or 8 on the WHO Ordinal Scale for Clinical Improvement at Day 15, Day 22, and Day 29

As the primary endpoint will be using WHO scale to define responders/non-responders this analysis specified in the protocol would be corresponding to the primary endpoint. Primary endpoint analysis table will include Days 15, 22 and 29 which makes this analysis redundant. Therefore this secondary endpoint will be dropped out.

# 6.12.2.3 Proportion of subjects with normalization of fever and oxygen saturation through Day 15, Day 22, and Day 29.

The percentage of subjects with normalization of fever and oxygen saturation through Day 15, Day 22 and Day 29 (inclusive) will be summarized. A subject will be considered as a treatment success if fever normalization (body temperature < 37.0 °C) maintained for at least 24 hours AND peripheral capillary oxygen saturation (SpO2) >94% sustained for 24 hours is observed.

This analysis will compare the percentage of subjects that meet the composite endpoint at Day 15, Day 22, and Day 29.

Evaluation of the responder status will include all vital sign data and vital sign log data, and responder status will be evaluated at study days 15, 22 and 29 by checking if subject had normal temperature and SpO2 at least for the last 24 hours.

Responders are subjects who have fever normalization maintained for at least 24 hours AND peripheral capillary oxygen saturation (SpO2) >94% sustained for 24 hours is observed at the time of the visit.

Non-responders are subjects who died before the visit or do not meet both criteria of the endpoint (fever normalization and  $SpO_2>94\%$ ) at the time of the visit.

These endpoints will be analyzed using the same methodology as for the primary endpoint.

QMD Ref: Worldwide-TMP-ST-005-7.0 Effective: 12Aug2019 Governing QMD: Worldwide-SOP-ST-0		
Confidentiality Statement		
This document is the property of Worldwide Clinical Trials Inc. and may not be duplicated, copied, altered or removed from company without prior approval from Worldwide Quality Assurance or in compliance with Worldwide Standard Operating Procedures.		

Worldwide Clinical Trials Controlled Quality Management Document		
WORLDWIDE CLINICAL TRIALS	Sponsor:	Veru Inc.
	Protocol Number:	V0211901
STATISTICAL ANALYSIS PLAN. PHASE 2-3-4		

Separate analysis will be performed for each visit.

